11.1. Statistical design, method and analytical procedures

The primary objective will be evaluated by analysing the primary and secondary endpoints. These analyses are carried out by Medical Affairs, Coloplast A/S and are described in the following. The secondary objective regarding the [REDACTED] will be evaluated out by [REDACTED] and [REDACTED]

All baseline measurements, endpoints and other measurements (see Appendix 1 - Endpoints) will be summarized by descriptive statistics and/or listed. Endpoints and other measurements will be summarized by product, product type (1- or 2-pc) and visit, if relevant. Descriptive statistics for continuous variables are presented with N, Mean, SD (standard deviation), Median, Min and Max), where N denotes the number of subjects contributing with non-missing data. For discrete variables, descriptive statistics are presented with N and percentage, where percentage is based on the total number of subjects/observations with non-missing data.

As it is an exploratory study no adjustment for multiple testing will be applied.

All statistical analyses are made with SAS version 9.4 (SAS Institute Inc., Cary, NC)

Definition of analysis populations

Intention to Treat (ITT), Safety and Per Protocol (PP) populations will be defined at a formal data review meeting just before database lock. As a minimum, the data manager, the clinical manager and the statistician will be involved in the classification of subjects.

The ITT population (full analysis set) will be constituted by all randomised subjects with valid informed consent who have been exposed to at least one product, and with valid information on at least one product with respect to either primary or secondary endpoints.

The PP population will be constituted by a subset of ITT subjects who fulfilled the inclusion/exclusion criteria and did not violate the protocol in a serious way

Any exclusion of subjects from the PP/ITT population must be documented. Invalid individual data points may be omitted from analysis even though the corresponding subject is part of the ITT or PP population. Any exclusion of data points will be documented.

The Safety population will constitute by subjects who have given informed consent.

All statistical analysis will be based upon the ITT and PP population whereas adverse events and Device deficiencies will be assessed based on the safety population.

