Type of endpoint	Group of endpoint	Description of Measurement endpoint	Derived from	Origin	Assessed by	V1	V2	V3	Calls	Product change
Reason for change		(You may tick more than one box)								
		What was the main reason for changing the products? (14 choices + other text)	App							
		
 - I followed my usual changing pattern - I thought it would be nice with a clean product - In preparation of an activity (i.e. going out, doing sports, travelling) - The entire baseplate had become detached - The outer edge of the baseplate had become detached - The centre of the baseplate had become detached - I was afraid the baseplate would become detached - The area around the stoma was itching - The area around the stoma was painful - There was leakage underneath and outside the baseplate - There was leakage underneath the baseplate (but not outside the baseplate) 	Subject							

CONFIDENTIAL

Type of endpoint	Group of endpoint	Description of measurement	Derived from	Origin	Assessed by	V1	V2	V3	Calls	Product change
			
 - The bag was full of air (ballooning) - There was vacuum in the bag (pancaking) - Due to test visit in the investigation - Other reason (text) 							
		Was there leakage outside the baseplate? (Yes/no) by baseplate change at steady state	Was there leakage outside the baseplate (i.e. soiling the clothes)? (Yes/no)	APP					Subject	
		Accessories used? by baseplate change at steady state	Which stoma accessories did you use?	APP					Subject	
			
 - Adhesive remover - Paste - Rings - Wipes - Stoma tape - Stoma belt - Hernia belt - Stoma powder - Barrier lotion/crème/spray/wipes - Cleansing wipes/cleansing spray - Odour remover - Other accessories (text) 							
										(You may tick more than one box)

CONFIDENTIAL

Type of endpoint	Group of endpoint	Description of Measurement	Derived from	Origin	Assessed by	V1	V2	V3	Calls	Product change
	Ballooning	Experience ballooning? (Yes/No) by each baseplate change at steady state	Did you experience the bag becoming overfilled with air during use (ballooning)? (Yes/No) If yes, how much did your bag become overfilled? (Not at all to very much)		Subject					X
Wear time		36. Median wear time (hours) by treatment at steady state	The median wear time is calculated by summary statistics of the individual wear times of each baseplate		Sponsor					X

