22.4. Appendix 4 – Baseline data

Baseline data – registered at the inclusion visit (V1) by Principal Investigator, or a delegate.

- Date of Informed Consent (date)
- Date of visit (date)
- Check of inclusion criteria
- Check of exclusion criteria
- Subject number (number - automatically generated in eCRF)
- Randomisation number (number - automatically generated in eCRF)
- Name/type of randomised product (list of investigational products)

Demographic

- Date of birth (date)
- Gender (male/female)
- Height (number - cm)
- Weight (number – kg)

Stoma

- Age of stoma (month (if available) and year when created)
- Type of stoma (ileostomy/colostomy)
- Cause of the stoma (Crohn's disease/Colitis ulcerosa/ Cancer/ Other)
- Size of the stoma (diameter on widest place and height)
- Shape of the stoma/intestine (round/oval/irregular)

Current product

- What is your Current product (brand, product name, item number, size, product type (1-piece/2-piece))?
- Are you used to cutting the baseplate? (Yes/No)
 - If yes, how much is cut off from the baseplate (*min and max cut in mm?*)
- Which stoma accessories do you normally use? (*You may tick more than one box*) (None, Adhesive remover, Paste, Rings, stoma tape, stoma belt, Hernia belt, Stoma powder, Barrier lotion, barrier cream, barrier spray or barrier wipes, Cleansing wipes/cleansing spray, Odour remover, Other accessories)
 - If 'other accessories', please specify
- On average, how often do you normally change your product (1pc)/baseplate (2pc)? (Once or more per day, Every second day, Every third day, Every fourth day, Every fifth day, Every sixth day, Once a week or less frequent)

CONFIDENTIAL

Peristomal skin area

- How often do you experience peristomal skin complications (itching, burning, red or discoloured skin, pain, bleeding, moist or broken skin)? (Daily, Every 2-3 days, every 4-6 days, Once a week, Once every second week, More rarely)
- Which peristomal skin complication/symptom do you experience most often? (itching, burning, red/discoloured skin, pain, bleeding, moist or broken skin)
- Body profile with body check tool
- How many times in the last year have you had a peristomal skin complication, where you had to seek consultation and/or treatment from a health care professional?

Leakage/output

- What is the frequency of your output? (All the time (continuous)/with regular intervals/with irregular intervals)
- Bristol scale score
- Do you experience ballooning (air in the bag)? (Yes/no)

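### The per-change accessory question in the app has no 'None' answer, so a change made without accessories cannot be told apart from an unanswered item

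*Combined protocol and SAP*

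**What the plan says.** Section 4.4.2 names use of accessories as an explorative endpoint group, and section 7.1.3 has the subject report it in the app at every product or baseplate change. In Appendix 1 the measurement is "Accessories used? by baseplate change at steady state", derived from the question "Which stoma accessories did you use". Several boxes may be ticked. The list starts "Adhesive remover - Paste - Rings - Wipes - Stoma tape - Stoma belt - Hernia belt - Stoma powder", goes on to a barrier-product option, a cleansing option and odour remover, and ends with a free-text 'other'. That makes eleven named accessories plus 'other'. No option means 'none', and no Yes/No question is shown before it.

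The baseline item in Appendix 4 asks which accessories the subject normally uses. Its options start "None, Adhesive remover, Paste, Rings, stoma tape, stoma belt".

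On reporting, section 11.1 says: "For discrete variables, descriptive statistics are presented with N and percentage", and the "percentage is based on the total number of subjects/observations with non-missing data". Accessory use has no model or test in section 11.1. In Appendix 1 it carries no endpoint number, so it is a measurement to be summarised or listed.

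**The concern.** A multi-tick list without a negative answer yields one kind of empty record for two different facts: no accessory was used, or the question was not answered. Other items completed at the same change avoid this. Ballooning and leakage outside the baseplate are Yes/No, and the itching-frequency item has a lowest category for no itching at all. The accessory item is the exception, although its baseline counterpart shows that the option was thought of.

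What is at stake is whether the accessory table can show a difference between the products, for instance users managing without accessories on one of them. The plan has no coding rule for an empty record, and once data are collected no analysis can recover the distinction.

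A related weakness is that the app list has a bare *Wipes* option beside the barrier option (which includes wipes) and the cleansing-wipe option. The baseline list has no bare *Wipes*. Section 7.4 does not allow barrier cream or film during the investigation, and this item is the only per-change record of barrier use that Appendix 1 shows. A barrier wipe logged as plain *Wipes* could not be identified.

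**Working it through.** The plan states no rate, power or sample size for accessory use, so there is no figure of its own to reproduce. The check is arithmetic on proportions under each possible coding of an empty record.

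**Inputs from the documents**
- Steady state is the last three weeks of each period, 21 days (Appendix 1).
- One change per day is expected for 1-piece users and two per three days for 2-piece users (section 5.1.6).
- 48 subjects per product type (section 6).
- Expected steady-state changes per product, before drop-out: 48 × 21 × 1 = 1008 (1-piece) and 48 × 21 × 2/3 = 672 (2-piece).

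**Assumptions (not in the documents)**
- True share of changes with any accessory, comparator versus test: 90% vs 70%, 60% vs 40%, or 50% vs 25%.
- Share of items genuinely skipped: 0% to 20%, unrelated to accessory use.

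**(a) Blank coded as missing.** Reported any-accessory percentage = changes with a tick / changes with a tick = 100%, always.

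| True use | Reported % | Counts, 1-piece, no skipping |
|---|---|---|
| 90% vs 70% | 100% vs 100% | 907 vs 706 |
| 60% vs 40% | 100% vs 100% | 605 vs 403 |
| 50% vs 25% | 100% vs 100% | 504 vs 252 |

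For a single accessory, reported % = true % / share of changes with any accessory. Take any use of 60% vs 40%, and paste at half of those changes. The true values are 0.5 × 60% = 30% and 0.5 × 40% = 20%; the reported values are 30/60 = 50% and 20/40 = 50%. If paste's share on the test product is 60% instead, the true value there is 0.6 × 40% = 24%. A fall from 30% to 24% is then reported as a rise from 50% to 60%.

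**(b) Blank coded as no accessory.** Reported % = true % × (1 − skipping rate).
- No skipping: 60% vs 40%, correct.
- 10% skipping on both: 0.60 × 0.90 = 54% and 0.40 × 0.90 = 36%.
- No true difference (60% on both), skipping 5% vs 20%: 0.60 × 0.95 = 57% and 0.60 × 0.80 = 48%, a false difference of 9 percentage points.

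**(c) App forces an answer.** The accessory-free user must tick something untrue or write 'none' under 'other', which may then be counted as use.

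**(d) Explicit *None*, denominator = answered changes.** Reported % = true % × (1 − skip) / (1 − skip) = true %. With 10% skipping, 0.54/0.90 = 60% and 0.36/0.90 = 40%. With 5% vs 20% skipping and no true difference, 0.57/0.95 = 60% and 0.48/0.80 = 60%.

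The percentages in (a), (b) and (d) do not depend on the number of changes, so they apply equally to 2-piece users.

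**The case against.** A reader might infer that section 11.1 itself removes accessory-free changes from the denominator, so that 100% versus 100% is what the plan prescribes. The documents do not support that. Section 11.1 restricts percentages to non-missing data but nowhere says that a completed change record with no accessory ticked is missing. If unticked boxes are stored as 'no', every record stays in and the difficulty is the one in (b). Even under (a), the counts are displayed, so a fall would not be wholly hidden, although counts also move with drop-out and with the number of changes.

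A reader might also infer that the missing option is what prevents comparison with baseline. It is not: baseline asks about habitual use per subject and the app about use at one change, so the two would differ in unit even with matching lists.

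Two further objections stand in part. The measurement is descriptive, and the rationale in section 4.4.3 does not mention accessories, so little depends on it. Appendix 1 is also damaged in extraction, and a gate question that exists only in the app cannot be excluded. But this list looks intact: the adjoining reason-for-change list has exactly the 14 choices plus 'other' that it announces.

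None of this removes the core point. The item as printed has no negative answer and the plan gives no coding rule.

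**Conclusion.** The point holds as an ambiguity in data collection. As printed, the app item cannot separate an accessory-free change from an unanswered one, and each way of handling the blank carries a different error. Coding it as missing fixes any-accessory use at 100% and inflates single-accessory percentages. Coding it as no use lets skipped items through, and in the example this creates a 9-point false difference. The sizes rest on assumed rates of use and skipping; if skipping were nil and blanks were coded as no use, there would be no error.

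The importance is low. Only a descriptive explorative measurement is affected, together with the usefulness of the item for identifying barrier products. It is worth raising because the repair is nearly free before the first subject starts and cannot be made by analysis afterwards.

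**What to change.** - Add *None* to the app's accessory list, as in Appendix 4, and make it exclusive of the other ticks; or put a Yes/No question in front of the list.
- Keep the existing denominator of answered changes and state that *None* (or 'No') counts as an answer. Do not switch to all logged changes, because that would count skipped items as accessory-free, as in (b).
- In the same edit, replace the bare *Wipes* by specific wipe types that do not overlap with the barrier and cleansing options, so that barrier use can be identified.

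The cost is one edit to the app list, one sentence in section 11.1 and one extra tap for the subject at an accessory-free change. If a gate question already exists in the app, showing it in Appendix 1 settles the main point. If the list can no longer be changed, the plan should state before database lock how an empty record is coded, and the report should give the number of empty records per product.

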22.2. Appendix 2 – Leakage scale questionnaire

Emotional impact

When you thought about your stoma device and the risk of leakage, what emotions did you feel?

In the last 7 days, due to leakage or worry about leakage...	All of the time	Often	Sometimes	Rarely or never
I felt panic	0	1	2	3
I felt stressed out	0	1	2	3
I felt more afraid about leaks in the future	0	1	2	3
I felt worry	0	1	2	3
I felt frustrated	0	1	2	3
I felt embarrassed	0	1	2	3
I felt worried that I might leak	0	1	2	3
I couldn't sleep	0	1	2	3
I kept waking up at night to check my stoma	0	1	2	3
I kept checking my stoma bag to see if I have leaked	0	1	2	3

Usual and Social activities

When you thought about your stoma device and the risk of leakage, how did it affect your activities?

In the last 7 days due to leakage or worry about leakage...	All of the time	Often	Sometimes	Rarely or never	Not applicable
I decided to stay at home	0	1	2	3	9
I couldn't do light activities	0	1	2	3	9
I changed my plans	0	1	2	3	9
I was unable to go out and meet family and friends	0	1	2	3	9
I avoided close physical contact with family and friends	0	1	2	3	9
I did not want to see people	0	1	2	3	9
I avoided people	0	1	2	3	9
I tried to avoid meeting new people	0	1	2	3	9

Coping and in control

When you thought about your stoma device and the risk of leakage, how did it affect your ability to cope?

In the last 7 days, due to leakage or worry about leakage...	All of the time	Often	Sometimes	Rarely or never
I felt in control	0	1	2	3
I was able to cope	0	1	2	3
I felt calm	0	1	2	3
I saw my friends as I usually do	0	1	2	3

CONFIDENTIAL

22.3. Appendix 3 - Quality of life questionnaire

This questionnaire asks you about the use of the stoma appliance from this test period and your experiences. You will be asked questions about the discreetness of the stoma appliance, comfort relating to wearing the stoma appliance, confidence you have with the stoma appliance, and how the device impacts your social life.

Please think about your experience with using the stoma appliance **during the past seven days** and please select the box that is closest to your current situation. There are no right or wrong answers. We want to understand how beneficial you think the stoma appliance is and also what problems you may have experienced with it.

For each of the statements, think about how the specific issue affects you. Please answer **ALL** questions as honestly as you can, and **please remember to answer the questions in relation to the past seven days only.**

Discreetness	Confidence

1. It was difficult to hide the stoma appliance under clothing
 
2. I was self-conscious about the appearance of the stoma appliance
 
3. The stoma appliance limited the choice of clothes that I could wear
 
4. The stoma appliance was obvious to other people
 
5. The color of the stoma appliance was discreet
 
6. It was difficult to hide the stoma appliance because of ballooning
	
1. I was confident that the stoma appliance would not leak
 
2. I worried that the stoma appliance would become loose from my body
 
3. I felt confident that I could spend the night away from home despite wearing the stoma appliance
 
4. I was confident the stoma appliance would not cause any problems for me
 
5. I felt confident to take part in physical activities (for example, sports) whilst wearing the stoma appliance
 
6. I worried that the stoma appliance would make a rustling noise.

Comfort	Social life

1. The stoma appliance was comfortable to wear
 
2. I was not concerned about skin irritation under the stoma appliance (for example, feelings of burning, itching, pinching or pain)
 
3. It was uncomfortable to remove the stoma appliance from my body
 
4. I often forgot that I was wearing the stoma appliance
 
5. The stoma appliance was comfortable as it fitted well to my body
 
6. The stoma appliance disrupted my sleep during the night
	
1. I worried that my family and friends felt awkward around me because of the stoma appliance
 
2. I felt my social life had been restricted because of the stoma appliance
 
3. I avoided close physical contact with family and friends because of the stoma appliance
 
4. I worried about whether I could have a relationship because of my stoma appliance
 
5. I worried about whether the stoma appliance would affect my sex life

CONFIDENTIAL

22.4. Appendix 4 – Baseline data

Baseline data – registered at the inclusion visit (V1) by Principal Investigator, or a delegate.

- Date of Informed Consent (date)
- Date of visit (date)
- Check of inclusion criteria
- Check of exclusion criteria
- Subject number (number - automatically generated in eCRF)
- Randomisation number (number - automatically generated in eCRF)
- Name/type of randomised product (list of investigational products)

Demographic

- Date of birth (date)
- Gender (male/female)
- Height (number - cm)
- Weight (number – kg)

Stoma

- Age of stoma (month (if available) and year when created)
- Type of stoma (ileostomy/colostomy)
- Cause of the stoma (Crohn's disease/Colitis ulcerosa/ Cancer/ Other)
- Size of the stoma (diameter on widest place and height)
- Shape of the stoma/intestine (round/oval/irregular)

Current product

- What is your Current product (brand, product name, item number, size, product type (1-piece/2-piece))?
- Are you used to cutting the baseplate? (Yes/No)
 - If yes, how much is cut off from the baseplate (*min and max cut in mm?*)
- Which stoma accessories do you normally use? (*You may tick more than one box*) (None, Adhesive remover, Paste, Rings, stoma tape, stoma belt, Hernia belt, Stoma powder, Barrier lotion, barrier cream, barrier spray or barrier wipes, Cleansing wipes/cleansing spray, Odour remover, Other accessories)
 - If 'other accessories', please specify
- On average, how often do you normally change your product (1pc)/baseplate (2pc)? (Once or more per day, Every second day, Every third day, Every fourth day, Every fifth day, Every sixth day, Once a week or less frequent)

CONFIDENTIAL

Peristomal skin area

- How often do you experience peristomal skin complications (itching, burning, red or discoloured skin, pain, bleeding, moist or broken skin)? (Daily, Every 2-3 days, every 4-6 days, Once a week, Once every second week, More rarely)
- Which peristomal skin complication/symptom do you experience most often? (itching, burning, red/discoloured skin, pain, bleeding, moist or broken skin)
- Body profile with body check tool
- How many times in the last year have you had a peristomal skin complication, where you had to seek consultation and/or treatment from a health care professional?

Leakage/output

- What is the frequency of your output? (All the time (continuous)/with regular intervals/with irregular intervals)
- Bristol scale score
- Do you experience ballooning (air in the bag)? (Yes/no)

CONFIDENTIAL

22.5. Appendix 5 - Bristol scale

Type 1	Type 2	Type 3	Type 4	Type 5	Type 6	Type 7
Separate hard lumps, like nuts (hard to pass)						
Sausage-shaped but lumpy						
Like a sausage but with cracks on its surface						
Like a sausage or snake, smooth and soft						

CONFIDENTIAL

22.6. Appendix 6 – Classification of leakage

[figure not shown]

Figure 1

Figure 2

Figure 3

Not considered leakage
The adhesive change
colour and swells due
to absorption of
moisture
(Figure 1)

Considered Leakage
Output under the microscope (with or without scaling the colonies)
(Figure 2, 3, 4 and 5)

[figure not shown]

Figure 4

Figure 5

Figure 5

CONFIDENTIAL

Approved

02-Sep-2019 11:08:27 GMT+0000

Approved

02-Sep-2019 11:42:24 GMT+0000
